6.1. Inclusion Criteria

Participants will be eligible for inclusion in this study only if all of the following criteria apply at **screening (Week -4 and Week -2)** and **randomization (Day 1)**, unless otherwise specified:

Age

1. ≥ 18 years of age at the time of signing the informed consent.

Type of Participant and Disease Characteristics

2. **CKD:** Have CKD, confirmed at screening: Kidney Disease Outcomes Quality Initiative (KDOQI) CKD stages 3, 4, or 5 defined by Estimated glomerular filtration rate (eGFR) using the CKD Epidemiology Collaboration (CKD-EPI) formula [Levey, 2009].
3. **Hgb:** Stable HemoCue Hgb from 8.5 to 10.5 at screening visit (Week -4) and from 8.5 to 10.0 g/dL at randomization (Day 1) (Section 9.1).
4. **IV Iron:** Participants may receive up to one IV iron dose within the 8 weeks prior to screening and NO IV iron use between screening visit and randomization (Day 1).
5. **Oral Iron:** If needed, participant may be on stable maintenance oral iron supplementation. There should be $<50\%$ change in overall dose and no change in type of iron prescribed doses in the 4 weeks prior to Day 1 randomization visit.

Sex

6. Male and female participants are eligible. A female participant is eligible to participate if she is not pregnant (see Section 12.4), not breastfeeding, and at least one of the following conditions applies:
 - Not a woman of childbearing potential (WOCBP) as defined in Section 12.4 (Appendix 4), or
 - A WOCBP who agrees to follow the contraceptive guidance in Appendix 4 during the treatment period and for at least 4 weeks after the last dose of study treatment.

Informed Consent

7. Capable of giving signed informed consent as described in Section 12.2 Appendix 2 which includes compliance with the requirements and restrictions listed in the informed consent form (ICF) and in this protocol.

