7.3. Method of Treatment Assignment

- Subjects will be stratified by region (Section 12.8 Appendix 8). Region at study entry is considered a stratification factor that is potentially prognostic of study endpoints. Following stratification all participants will be centrally randomized in a 1:1 fashion to receive either oral daprodustat or oral placebo.
- Once a randomization number has been assigned by the IRT system, it must not be re-assigned
- Study treatment will be dispensed at the study visits summarized in the SoA (Section 2).
- Returned study treatment should not be re-dispensed to the participants.

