7.7.2. Rescue Criteria

A rescue algorithm is provided to minimize participants having an inadequate response to the treatment for their anemia for an extended period of time and to enable consistency in the application of rescue therapy across the study. Details are provided in [Table 7](#).

This rescue algorithm **does not** apply to participants with low Hgb as a result of an acute or subacute event with an identifiable cause (e.g., GI bleed, blood loss due to surgery or vascular access). In these cases, treatment should be directed to the specific cause and randomized treatment will be continued at the current dose (unless Hgb is ≥ 13 g/dL which requires a dose hold).

Table 7 Rescue Algorithm for Anemia Management

Evaluate Participant for Rescue starting from Week 4 if:	

 • HemoCue Hgb is <7.5g/dL, or • HemoCue Hgb is <8.5g/dL and participant is symptomatic¹, or • HemoCue Hgb is <8.5 g/dL on three consecutive visits 	
Step 1: Initial Intervention	
Initial intervention depends on the participant's iron status:
 
 • If participant has TSAT < 15% and/or Ferritin < 50 ng/mL from a prior study visit, then 
 ○ continue with study treatment, and ○ intervene with iron therapy: Single dose of IV iron up to 1000 mg (in addition to the iron management criteria) 
At the next study visit in 4 ±1 weeks, recheck HemoCue Hgb. If HemoCue Hgb value continues to meet the evaluation criteria for rescue, then Proceed to Step 2.
 
 • If participant has TSAT ≥15% and Ferritin ≥ 50ng/mL, proceed to step 2.
Step 2: Rescue	
Randomized treatment should be permanently discontinued (but participant should remain in study to monitor Hgb) and the participant should be rescued according to local clinical practice:
 
 • If HemoCue Hgb remains <8.5 g/dL despite Initial Intervention (Step 1) based on the average of two HemoCue Hgb values ² • Rescue can be considered IV iron, rhEPOs and/or Transfusions.

1. Symptoms should be related to anemia of CKD. Further information regarding collecting this data will be stated in the SRM.

2. Repeat HemoCue Hgb at the same study visit to confirm Hgb (using the same sample); take average of 2 values.

The study site will supply any rescue medication that will be obtained locally.

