10.2. Sample Size Determination

10.2.1. Sample Size Assumptions

The sample size of this study has been primarily determined in order to achieve sufficient power for the principal secondary endpoint SF-36 vitality sub-score, since the anticipated effect size of this endpoint is less than that for the primary endpoint.

Approximately 600 participants are planned to be randomized (300 per arm) to receive daprodustat or placebo, who will be treated to achieve and maintain Hgb between 11 and 12 g/dL. Under the assumption that up to 10% of participants will withdraw from the study before Week 24 (start of EP), 600 randomized participants will result in at least 540 evaluable participants.

For the primary endpoint, the expected difference in mean Hgb change from baseline and the EP, between arms, is 1.0 g/dL and the anticipated between participant standard deviation (SD) is 1.5 g/dL, based on historical rhEPO trials and daprodustat clinical trial experience to date. The planned study size provides more than 99% power for superiority. In addition, it is anticipated that the smallest difference in mean Hgb change between arms that would meet the statistical criterion for superiority would be 0.25 g/dL.

For the first principal secondary endpoint of % of participants having a Hgb increase of ≥ 1.0 g/dL from baseline to EP, 540 evaluable participants provides $>90\%$ power to detect a 20% difference between daprodustat and placebo, assuming 30% of placebo arm participants will have a Hgb increase of ≥ 1.0 g/dL. In that case the smallest difference between daprodustat and placebo that would meet the statistical criterion for superiority would be 8%.

For the second principal secondary endpoint of mean change in SF-36 vitality sub-score between baseline and week 28, 540 evaluable participants provides for 79% power to detect a difference between arms under the assumption of a between treatment effect of 5 points in favor of daprodustat and a within-group standard deviation of 21 points. Prior research has determined that anemia is associated with a difference of 5.4 points from baseline for SF-36 vitality scores (Bjorner, 2007). It is expected that the smallest difference between arms that would meet the statistical criterion for superiority in this principal secondary endpoint is 3.5 points.

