5.2. Baseline Definitions and Derivations

5.2.1. Baseline Definitions

For all endpoints the baseline value will be the latest non-missing pre-dose assessment on or before the randomization date (except as noted below). This is generally expected to be the pre-dose value from the Day 1 visit, although such values may be missing.

| Parameter | Study Assessments Considered As Baseline | | | Baseline Used in Data Display |
|---|--|----------------|------------------|-------------------------------|
| | Screen Week -4 | Screen Week -2 | Day 1 (Pre-Dose) | |
| Efficacy | | | | |
| Hgb ^[1] | | | X | Day 1 |
| Iron Parameters | | | X | Day 1 |
| Monthly Oral iron ¹ | | | X | Day 1 |
| Monthly IV iron ² | | | X | Day 1 |
| Estimated Glomerular Filtration Rate (eGFR) | | | X | Day 1 |
| Serum Creatinine | | | X | Day 1 |
| Safety | | | | |
| SBP/DBP and HR | | | X | Day 1 |
| Lipid Parameters, Clinical Chemistry, Hematology, Other Laboratory, and Hepatobiliary (liver) Tests | | | X | Day 1 |
| PRO | | | | |
| Actigraphy | | | X | Day 1 |
| SF-36 Domain and | | | X | Day 1 |

CONFIDENTIAL

205270

| Parameter | Study Assessments Considered As Baseline | | | Baseline Used in Data Display |
|------------------|--|----------------|------------------|-------------------------------|
| | Screen Week -4 | Screen Week -2 | Day 1 (Pre-Dose) | |
| Component Scores | | | | |
| CKD-AQ | | | X | Day 1 |
| WPAI-ANS-CPV | | | X | Day 1 |
| EQ-5D-5L & VAS | | | X | Day 1 |
| PGI-S | | | X | Day 1 |
| PGI-C | | | X | Day 1 |

NOTES:

- Unless otherwise stated, the mean of replicate assessments at any given time point will be used as the value for that time point.

[1] Baseline monthly oral iron dose will be defined as total oral iron (mg) over the 4 weeks prior to randomization. See Section 10.6.3.

[2] Baseline IV monthly iron dose will be defined as total IV iron (mg) over the 8 weeks prior to screening, since participants may only receive up to one IV iron dose within the 8 weeks prior to screening and no IV iron use between screening visit and randomization. See Section 10.6.3.

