5.4. Examination of Covariates, Other Strata and Subgroups

- The following is a non-exhaustive list of covariates that may be used in summaries of demographics, descriptive summaries and statistical analyses.
- Additional covariates of clinical interest may also be considered.
- If the percentage of participants is small within a particular subgroup, then the subgroup categories may be refined prior to unblinding the trial.
 - If the category cannot be refined further, then descriptive rather than statistical comparisons may be performed for the particular subgroup
- The primary and principal secondary endpoints will be evaluated for a set of prespecified subgroups. Subgroup analyses are aimed to assess for consistency with the overall result, and they may have low power if the subgroup is small. Statistical models (ANCOVA or CMH chi-squared test) will be adjusted for the covariates used in the original analysis, subgroup, treatment and treatment by subgroup interaction. Point estimates and two-sided 95% CIs will be estimated (presented on Forest Plots) and the subgroup by treatment interaction p-value calculated. Subgroup analyses will not be adjusted for multiplicity.

| Subgroups (Based on status before randomization) | Categories |
|--|--|
| Age | <65 years, ≥65 years - <75 years, ≥75 years |
| Gender | Female, Male |
| Race Group | Summary tables: American Indian or Alaskan Native, Asian, Black, Native Hawaiian or Other Pacific Islander, White, Mixed Race Analysis: American Indian or Alaskan Native, Asian, Black, White (exclude Native Hawaiian or Other Pacific Islander and Mixed Race) |
| Ethnicity | Hispanic, non-Hispanic |
| Region | Per Section 5.3 |
| Baseline BMI | <30kg/m ² , ≥30kg/m ² |

CONFIDENTIAL

205270

| Subgroups (Based on status before randomization) | Categories |
|--|---|
| Baseline Weight | <75kg, ≥75kg |
| Baseline Hgb | <8.5g/dL, 8.5-<9g/dL, 9-10g/dL, > 10g/dL <9g/dL, 9-<10g/dL, 10-11g/dL, >11g/dL |
| Serum Iron Levels at Baseline | TSATs≥15% and Ferritin≥50 ng/mL vs TSATs<15% or Ferritin<50 ng/mL |
| Iron Replete Participants | TSATs≥20% and Ferritin≥100 ng/mL vs TSATs<20% or Ferritin<100 ng/mL |
| hsCRP | Quartile Analysis |
| Diabetic | Yes, or No |
| History of Heart Failure | Yes, or No |
| eGFR | <15, ≥15 |
| ADPKD (Autosomal Dominant Polycystic Kidney Disease) | ADPKD, non-ADPKD Note: Only used for analyses of eGFR |

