- For the MMRM analysis of change from baseline in Hgb, an LSMEANS statement will provide adjusted treatment group means and standard errors and a point estimate and two-sided 95% confidence interval for the adjusted mean treatment difference (daprodustat - placebo) at Week 28. The one-sided non-inferiority p-value for this test will be calculated.

Model Results Interpretation

- For the responder analysis, the one-sided CMH p-value will be compared to 0.025 to assess nominal significance.
- For the percent time in range analysis, a nominal superiority will be achieved if the lower limit of the two-sided 95% CI is above 0 and the one-sided p-value is < 0.025
- For the MMRM analysis of change from baseline in Hgb, superiority will be achieved if the lower limit of the two-sided 95% CI is above 0 and the one-sided p-value is < 0.025

Time to Rescue

| |
|---|
| Secondary Efficacy Statistical Analyses: Time to Rescue |
| Endpoint / Variables |
| 
 Time to stopping study treatment due to meeting rescue criteria |
| Model Specification |
| 
 The Cox Proportional Hazards model will adjust for the following baseline categorical values: 
 Treatment Region (as randomized, see Section 5.3) Confidence intervals for the rate per 100 person-years will also be reported. For within-group rates, the two-sided 95% CI will be obtained using an exact Poisson method. For difference in rates between treatments, the two-sided 95% CI will be constructed with a Normal approximation using Wald's method [Liu, 2006]. Analysis will include only those efficacy endpoints occurring within the time period for treatment discontinuation. Calculation of time-to-event or censoring is described in further detail in Section 10.6.3. Time to stopping study medication due to meeting rescue criteria is defined as the time from Randomization until the date on which a participant permanently stops study medication due to meeting criteria for rescue. |
| Model Results Presentation |

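### The time-to-rescue Cox model leaves out baseline Hgb, which is already collected and should be prognostic: a small gain for one line of SAP text

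*SAP*

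**What the plan says.** **The model.** For time to permanent discontinuation because rescue criteria were met, SAP 7.3.2.1 states: "The Cox Proportional Hazards model will adjust for the following baseline categorical values". Treatment and region as randomized follow. SAP 10.6.3 defines the event date, censoring and rates for this endpoint and adds no covariate. The one-sided p-value is compared with 0.025 nominally, and SAP 5.5 places the endpoint outside the hierarchy.

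**The event.** Protocol 7.7.2 (Table 7) starts evaluation for rescue at HemoCue Hgb below 7.5 g/dL, below 8.5 with symptoms, or when "HemoCue Hgb is <8.5 g/dL on three consecutive visits". Step 2 stops treatment: "If HemoCue Hgb remains <8.5 g/dL despite Initial Intervention (Step 1".

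**Entry and allocation.** Inclusion criterion 3 requires Hgb "from 8.5 to 10.0 g/dL at randomization (Day 1". On randomization, Protocol 7.3 says "Subjects will be stratified by region" and names no Hgb stratum.

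**Baseline Hgb.** SAP 5.2.1 defines it: "For all endpoints the baseline value will be the latest non-missing pre-dose assessment on or before the randomization date". The imputation notes in SAP 10.6.3 say that nobody can be randomized without one. The primary ANCOVA (SAP 7.1.5.1) and the Hgb MMRM (SAP 7.3.2.1) both adjust for it. SAP 5.4 describes its list, which includes baseline Hgb, as a "non-exhaustive list of covariates that may be used in summaries of demographics, descriptive summaries and statistical analyses". That is permission and does not put the variable into this model.

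**The concern.** A participant who enters at 8.5 g/dL starts at the rescue threshold; one who enters at 10.0 starts 1.5 g/dL above it. Few covariates are so directly tied to an event, yet the model omits this one. Two things follow.

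- Any chance difference between arms in baseline Hgb stays in the reported hazard ratio.
- If the drug effect on rescue is small, some power is lost. In a Cox model, omitting a prognostic covariate pulls the log hazard ratio towards zero.

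Validity is not at stake, because randomization protects the unadjusted test. Adding the covariate after unblinding, on the strength of SAP 5.4, would be a post hoc choice.

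**Working it through.** **Plan's own figure.** The documents give no power, event count or hazard ratio for time to rescue. The trial is sized on SF-36 vitality (Protocol 10.2.1). With 270 per arm, difference 5 and SD 21: 5 / (21 × √(2/270)) = 2.77; 2.77 − 1.96 = 0.81; Φ(0.81) = 0.79. This matches the stated 79%.

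**Inputs from the documents.** 600 randomized 1:1, up to 10% withdrawal, entry range 8.5–10.0 g/dL, the Table 7 triggers, planned effect 1.0 g/dL, and "the anticipated between participant standard deviation (SD) is 1.5 g/dL" for change in Hgb.

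**Assumed inputs (not in the documents).**
- Usual Hgb mean 9.5, SD 0.8, kept if Day 1 HemoCue is 8.5–10.0.
- Visit-to-visit SD 0.5 (range 0.3–0.7); HemoCue error SD 0.25.
- 40% symptomatic when below 8.5 (20–60%); 20% iron-deficient at the trigger (0–40%).
- Between-participant drift (three shapes) set so that placebo change has SD 1.46–1.50.
- Drug effect at full size by Week 12. Any Hgb rise from the IV iron itself is not modelled.

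**Prognostic strength with no drug effect.** Rescue occurs in 29%: 42% with Day 1 Hgb below 9 and 25% with 9–10. The hazard ratio per +1 g/dL of baseline Hgb is 0.41 (0.32–0.53 over the ranges; 0.20 if the SD of change were only 0.6).

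**Effect of chance imbalance.**
1. If Hgb were uniform over 8.5–10.0, its SD would be 1.5/√12 = 0.43. A 1-in-20 imbalance is then 1.96 × 0.43 × √(2/300) = 0.07 g/dL. The simulation gives 0.07 on HemoCue and 0.08 on central-laboratory values.
2. Shift in log HR: 0.07 to 0.08 × |ln 0.41| = 0.06 to 0.07, a factor of 1.06 to 1.07. The simulation agrees (6–7%; 4–10% over the ranges; 11–12% if the SD of change is 0.6).
3. Events: 0.29 × 600 = 174, so SE(log HR) ≈ 2/√174 = 0.15. The shift is about 0.4 of an SE.
4. The correlation between the log HR and this imbalance is about −0.2 unadjusted and about 0 adjusted.

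**One-sided rejection at 0.025.**

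| Drug effect (g/dL) | Treatment + region | + baseline Hgb | Gain (points) |
|---|---|---|---|
| 0 | 2.6% | 2.6% | 0 |
| 0.15 | 17.2% | 18.5% | 1.3 |
| 0.25 | 40.2% | 42.5% | 2.3 |
| 0.4 | 76.5% | 79.6% | 3.1 |
| 0.6 | 97.5% | 98.0% | 0.5 |
| 1.0 (planned) | 100% | 100% | 0 |

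Over the input ranges the gain at 0.25–0.4 g/dL is 0.7 to 4.6 points (Monte Carlo SE about 0.5). With Table 4 starting doses and approximate Table 6 titration it is 0.9 to 2.4 points at effects of 0.20–0.49 g/dL, and 0 at 0.92. The median HR hardly moves: 0.76 unadjusted and 0.75 adjusted at 0.25 g/dL; 0.31 and 0.30 at 1.0.

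**Second check, a different model.** Exponential event times with assumed placebo rescue of 10% or 20%; 1,500 trials per row.

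| Placebo rescue | Treatment HR | HR per g/dL | SD of baseline Hgb | Without | With |
|---|---|---|---|---|---|
| 10% | 0.5 | 0.5 | 0.45 | 57.5% | 59.1% |
| 20% | 0.5 | 0.5 | 0.45 | 87.3% | 87.3% |
| 10% | 0.5 | 0.25 | 0.45 | 59.3% | 60.4% |
| 20% | 0.5 | 0.25 | 0.45 | 88.0% | 89.5% |
| 10% | 0.5 | 0.25 | 0.6 | 57.2% | 58.3% |
| 20% | 0.5 | 0.25 | 0.6 | 85.8% | 89.9% |
| 20% | 0.6 | 0.15 | 0.6 | 58.3% | 70.7% |
| 20% | 0.6 | 1.0 (not prognostic) | 0.6 | 67.3% | 67.3% |
| 20% | 1.0 (null) | 0.25 | 0.6 | 2.1% | 2.1% |

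Only the 0.5 rows fall inside the 0.32–0.53 range found above; they gain 1.6 and 0 points. The 12-point gain needs an HR of 0.15 per g/dL, well outside that range, and should not be relied on. Adjustment costs no power when Hgb is not prognostic.

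**The case against.** The strongest reply is that nothing is broken.

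- **No decision depends on it.** The test is valid, the endpoint is nominal, and at the planned 1.0 g/dL there is no power to gain. All of this stands.
- **The interval does not tighten.** A second programming of the threshold simulation gave 28% rescue and power of 40.5% against 42.6% at 0.25 g/dL, with a mean SE of the log HR of 0.165 in both models. This also stands. The gain comes from a slightly larger log HR and from removing imbalance, not from a smaller SE.
- **The plan has a convention.** Its CMH analyses adjust for treatment and region only, and baseline values enter the continuous-outcome models. That is a fair description, but a CMH test needs strata, whereas a Cox model takes a continuous covariate directly.
- **Imbalance would be visible.** Baseline Hgb categories are tabulated by arm (SAP 6.2.4). True, but seeing an imbalance does not remove it from the estimate.
- **The HR becomes conditional.** The rates and rate difference in the same display stay unadjusted. Baseline Hgb also sets the starting dose (Protocol Table 4), so the effect may vary with it. With the drug effect doubled below 9 g/dL, the gain was 4.6 points at 0.25 g/dL and 1.4 at 0.4.
- **Placebo drift may be upward.** Protocol 10.2.1 assumes 30% of placebo participants rise by at least 1.0 g/dL. With SD 1.5 that implies a mean change of 1.0 − 0.524 × 1.5 = +0.2 g/dL. Placebo rescue then falls to about 25%. The gain is 0.5 points at a 0.5 g/dL effect (89.2% to 89.7%) and still about 3 at 0.25 (800 trials, noisy).

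These objections limit the size of the point; they do not remove it.

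**Conclusion.** The concern holds as a minor, optional improvement. The omission, the link between the event and Hgb, the region-only stratification and the availability of baseline Hgb are all plain from the documents. The benefit is a hazard ratio free of baseline Hgb imbalance, plus roughly 1 to 5 points of power if the drug effect is well below plan. There is none at 1.0 g/dL and no Type I cost. Confidence in the size is medium, because the rescue rate, symptom rate, iron status and visit-level variability are all assumed. Symptoms and iron status also affect rescue, so Hgb is the main driver but not the only one.

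**What to change.** Before unblinding, amend the Time to Rescue specification in SAP 7.3.2.1:

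- Add baseline Hgb as a continuous covariate alongside treatment and region, using the default definition in SAP 5.2 and 10.6.3 (central laboratory, HemoCue if missing). No separate HemoCue baseline is needed.
- Remove the word categorical from the sentence that introduces the covariates.
- Label the reported hazard ratio as conditional on baseline Hgb and region.
- Leave the rescue rule, the incidence rates and the rate difference unchanged.

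The cost is one covariate, one line of text and a label. No new data, visits or participants are needed.

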15. France sites and participants with history of ADPKD only (to be performed at or after the week 28 study visit or as soon as clinically feasible prior to the Follow-up visit (see Section 9.5.4) for additional details).
16. For Argentinian sites **only** and only in WOCB
17. New doses of study treatment will be provided to participants starting from Day 1 to week 24 visit as indicated by IRT System. Study treatment may be dispensed at week 2 or unscheduled visit only if indicated by IRT system, otherwise participants should continue on study treatment dispensed at prior study visit.

Table 2 Schedule of Activities for Patient Reported Outcomes and Actigraphy

Protocol Activity (visits ± 1 week) (Note: All visit timings are relative to Day 1)	Screening Week -4	Week -2	Treatment Period: Day 1 through Week 28								Follow-up Visit
			Day 1	Week 4	Week 8	Week 12	Week 16	Week 20	Week 24	Week 28	
Dispense Actigraphy Device		X		X	X					X	
Actigraphy (wearable) ^{1,5,6}			X		X	X					X
Patient Global Impression of Severity (PGI-S) ^{2,3}		X	X		X	X					X
Patient Global Impression of Change (PGI-C) ^{2,3}					X	X					X
Symptoms of aCKD questionnaire ²		X	X		X	X					X
Short Form 36 (SF-36) ^{2,3}			X		X	X					X
EuroQol 5 Dimension 5 Level Health Utility Index (EQ-5D-5L) and EuroQol Visual Analogue Scale (EQ-VAS) ^{2,3,4}			X		X	X					X
Work Productivity and Activity Impairment Questionnaire (WPAI-ANS-CPV) ^{2,3}			X		X	X					X
Healthcare resource utilization (participants-reported)			X		X	X		X			X

1. Actigraphy device should be worn for 7 days prior to the study visits indicated in [Table 2](#) and as described in [Section 9.7](#). Data will be downloaded from device during the study visits indicated in [Table 2](#).
2. Patient reported outcomes questionnaire should be completed as the first assessment, prior to conducting any other visit assessments (e.g. Adverse event assessment, HemoCue Hgb, etc.)
3. Subjects who are unable to or require assistance to read must not complete the questionnaires
4. Only in selected countries. See [Section 12.8 \(Appendix 8\)](#).
5. Sites can contact subjects to wear the actigraphy device 7 days prior to study visit.
6. All efforts should be made to encourage participation in this activity monitoring assessment. If a participant is unable to take part, the reason should be documented, and they may continue in the study.

Table 3 Schedule of Activities for Participants Permanently Discontinuing Study Treatment

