7.2.5.2. Statistical Methodology Specification

| Endpoint / Variables |
|--|
| 
 • % of participants having a Hgb increase of ≥ 1.0 g/dL from baseline to EP. • Mean Change in SF-36 Vitality domain between baseline and Week 28 |
| Model Specification |
| 
 • For the first principal secondary endpoint of % of participants having a Hgb increase of ≥ 1.0 g/dL from baseline to EP, the EP Hgb value will be defined as the mean of all available Hgb values (on and off-treatment) during the EP (Week 24 to Week 28 inclusive). A Cochran-Mantel-Haenszel (CMH) chi-squared test, adjusting for treatment, and region (see Section 5.3), will be used to make comparisons between the treatment groups. A treatment policy strategy will be used in the analysis to include all on and off treatment Hgb values of the ITT populations, including values taken after rescue and IP discontinuation. • For the second principal secondary endpoint of mean change in SF-36 vitality sub-score |

CONFIDENTIAL

205270

between baseline and Week 28, a hypothetical strategy will be used which includes only on-treatment values and exclude the measures taken after IP disc/rescue medication. The SF-36 vitality sub-scores will be imputed if missing. An ANCOVA model will be used including factors for baseline score, treatment, and region.

Model Results Presentation

- For the first principal secondary endpoint, the number and % of participants having a Hgb (on and off-treatment) increase of ≥ 1.0 g/dL from baseline to EP by treatment group, relative response rate (daprodustat vs. placebo) and two-sided 95% CI will be provided along with the one-sided CMH p-value for the treatment group comparison.
- For the second principal secondary endpoint, each individual item within the SF-36 vitality subscore will be summarized using mean, standard deviation, minimum, P25, median, P75 and maximum at baseline, Week 8, Week 12, and Week 28 visit by treatment group. (See Section 7.3.2.1)
- For the second principal secondary endpoint, all available SF-36 vitality sub-score change from baseline values (on-treatment only) will also be summarized using mean, standard deviation, minimum, P25, median, P75, and maximum at Week 8, Week 12, and Week 28 visit. (See Section 7.3.2.1)

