| 
 • For the % of participants having an improvement in SF-36 Vitality Domain ≥ 6 from baseline at Week 28, a Cochran-Mantel-Haenszel (CMH) chi-squared test, adjusting for treatment and region (see Section 5.3), will be used to make comparisons between the treatment groups. This will be based on the traditional scoring. As in the second principal secondary endpoint, on-treatment SF-36 vitality sub-scores will be used, and exclude the measures taken after IP discontinuation. Subjects with missing SF-36 data will be imputed based on treatment status as described in Section 7.2.5.2. • Scoring for the SF-36 parameters and EQ-5D parameters is outlined in Section 10.6.5. • The mean change from baseline in SF-36 HRQoL scores (individual items of the Vitality Domain, overall score of the Physical Function Domain), EQ-5D-5L score, and EQ-VAS score will be analyzed using an MMRM approach with an unstructured covariance matrix to compare the difference in means between arms. The models will be fitted to HRQoL data collected after baseline up to Week 28, using on treatment values and exclude the measures taken after IP discontinuation. The model will include factors for treatment, time, region (See Section 5.3), treatment by time interaction, corresponding baseline value (HRQoL parameter or utility scores) and the baseline value by time interaction term. Analyses will be done with the MIXED procedure in SAS, using the Kenward-Roger option to estimate denominator degrees of freedom and standard errors. |
| Model Results Presentation |

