| 
 • One-sided p-values will be compared to 0.025 to assess nominal significance. • Clinically meaningful effects for PRO assessments focused on metrics that would be needed for a reimbursement agency or health technology assessment agency will be specified in a separate reimbursement RAP |

Work Productivity and Regular Daily Activity Impairment

| |
|---|
| Secondary Efficacy Statistical Analyses: Work Productivity and Regular Daily Activity Impairment |
| Endpoint / Variables |
| 
 • N (%) of patients currently employed on the WPAI-ANS-CPV • Change from baseline in percent and mean hours work time missed on the WPAI-ANS-CPV • Change from baseline in percent impaired (equivalent) on the WPAI-ANS-CPV • Change from baseline in overall percent work impairment (equivalent) on the WPAI-ANS-CPV • Change from baseline in percent activity impairment on the WPAI-ANS-CPV |
| Model Results Presentation |
| 
 • The summary statistics (mean, standard deviation, minimum, P25, median, P75, and maximum) will be provided by treatment group for each of the responses to the WPAI-ANS-CPV at all scheduled on treatment visits. • For the continuous responses to the WPAI-ANS-CPV, the change from baseline will be summarized by treatment group using mean, standard deviation, minimum, P25, median, P75, and maximum at all scheduled visits. |

Blood Pressure

| |
|--|
| Secondary Efficacy Statistical Analyses: Blood Pressure |
| Endpoint / Variables |
| 
 • Change from baseline in SBP, DBP, and MAP at week 28 • N (%) with at least one BP exacerbation event during the study |
| Model Specification |
| 
 • For the change from baseline in SBP, DBP, and MAP at week 28, a MMRM approach will be used with an unstructured covariance matrix to compare the difference in means between |

CONFIDENTIAL

205270

| |
|---|

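### The SF-36 Vitality ≥ 6-point responder test stratifies by region only; adding baseline vitality would gain roughly 4 to 8 points of power if the baseline–Week 28 correlation is 0.5

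*SAP*

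**What the plan says.** The responder endpoint is not in the protocol. The SAP adds it (Section 2.1, Table 1) and gives its test in Section 7.3.2.1: for the proportion with an "improvement in SF-36 Vitality Domain ≥ 6 from baseline at Week 28, a Cochran-Mantel-Haenszel (CMH) chi-squared test, adjusting for treatment and region". The score used is the 0–100 one: "This will be based on the traditional scoring". Missing scores are imputed as for the principal secondary endpoint. The display gives percentages by arm, a relative response rate with 95% CI and a one-sided CMH p-value. For interpretation, "One-sided p-values will be compared to 0.025 to assess nominal significance". SAP 5.5 places the endpoint outside the testing hierarchy. Table 2.50 is its only planned analysis.

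Other analyses of the same instrument use the baseline score:
- Principal secondary mean change in vitality (SAP 7.2.5.2): "An ANCOVA model will be used including factors for baseline score, treatment, and region".
- Repeated-measures models for the vitality items, Physical Function and EQ-5D, specified beside the responder test: "corresponding baseline value (HRQoL parameter or utility scores) and the baseline value by time interaction term".

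SF-36 is collected on Day 1 (Protocol Section 2, Table 2; SAP 5.2.1).

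**The concern.** Response is defined as a rise of at least 6 points, so it depends on where the participant starts. Low scorers tend to rise through regression to the mean, and anyone starting above 94 on a 0–100 scale cannot respond. Baseline vitality should therefore predict response within each region. A CMH test stratified by region alone leaves that predictable variation in the error term. The variable is already collected and already used for the continuous version of the same score, and the SAP gives no reason for omitting it here. What is at stake is the precision of one nominal secondary comparison.

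**Working it through.** **Inputs from the documents.** Effect 5 points, SD 21, 540 evaluable (270 per arm), 79% power for the mean change (Protocol 10.2.1); one-sided 2.5%; response = change ≥ 6 (SAP 7.3.2.1).

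**Assumed, because the documents are silent.** Baseline–Week 28 correlation ρ (0.3, 0.5, 0.7); placebo mean change (0 to 5 points); normal scores; equal SDs at both visits.

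**1. The plan's own figure.** Protocol 10.2.1 says "540 evaluable participants provides for 79% power to detect a difference between arms", assuming "a between treatment effect of 5 points in favor of daprodustat and a within-group standard deviation of 21 points". Noncentrality = 5 / (21 × √(2/270)) = 2.766. Power = Φ(2.766 − 1.96) = 79.0%. This reproduces.

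**2. Power of the region-only responder test.** With placebo mean change 3:
- Placebo response rate = 1 − Φ((6 − 3)/21) = 44.3%.
- Daprodustat response rate = 1 − Φ((6 − 8)/21) = 53.8%.
- Power for two proportions at 270 per arm = 59.6%.

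For placebo mean changes of 0 and 5 the result is 59.2% and 59.5%. Simulated region-stratified CMH gives 58–59%.

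**3. Link between baseline and response.** With equal SDs, the baseline–change correlation is −√((1 − ρ)/2): −0.59, −0.50 and −0.39 for ρ = 0.3, 0.5 and 0.7. At ρ = 0.5 the SD of change is 21 × √(2 × 0.5) = 21, so it does not matter there whether SD 21 means the score or its change. Dichotomising near 50% multiplies the correlation by about 0.798, giving r = 0.472, 0.399 and 0.309 with the yes/no response.

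**4. Power with baseline, by formula.** Unadjusted noncentrality from step 2 is 1.96 + Φ⁻¹(0.596) = 2.203. Adjusted power = Φ(2.203/√(1 − r²) − 1.96).

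| ρ | r | Calculation | Power with baseline | Gain |
|---|---|---|---|---|
| 0.3 | 0.472 | Φ(2.499 − 1.96) | 70.5% | +10.9 |
| 0.5 | 0.399 | Φ(2.402 − 1.96) | 67.1% | +7.5 |
| 0.7 | 0.309 | Φ(2.316 − 1.96) | 63.9% | +4.3 |

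**5. Simulation.** SD of change 21, placebo mean change 3, baseline mean 50, scores clipped to 0–100, five equal regions, 3,000 trials per setting. Each power has a Monte Carlo SE of about √(0.6 × 0.4/3000) = 0.9 points.

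| ρ | CMH, region | CMH, region × baseline quartile | Logistic, region + baseline |
|---|---|---|---|
| 0.3 | 60% | 69% | 71% |
| 0.5 | 58% | 63% | 66% |
| 0.7 | 58% | 62% | 64% |

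Further runs:
- Baseline–change correlation −0.5, 8,000 trials, placebo mean 0: 58.0% (region), 62.3% (region × median split), 63.4% (region × quartile), 65.6% (logistic). With placebo mean 5: 59.0%, 63.6%, 64.3%, 66.5%.
- Baseline–change correlation −0.6 (ρ = 1 − 2 × 0.36 = 0.28), placebo mean 0: 58.2% rises to 67.6% (quartile) or 70.4% (logistic).
- SD 21 read as the score SD, ρ = 0.7, scores bounded and rounded to assumed 6.25-point steps, placebo mean 0: 79.5% rises to 82.9% (quartile) or 84.2% (logistic).
- 300 per arm (all randomised), baseline–change correlation −0.5: 63% rises to 69% (quartile) or 71% (logistic).

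**6. Type I error.** With no treatment effect and a baseline–change correlation of −0.5, rejection rates lie between 2.3% and 2.7% with or without baseline.

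Multiple imputation was not simulated; 270 and 300 per arm bracket the information.

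**The case against.** The strongest reply is that nothing here is wrong. Under randomisation stratified by region, a region-stratified CMH test is valid, and chance baseline imbalance is ordinary sampling error that the confidence interval covers. Region-only CMH is also the SAP's convention: the Hgb increase, Hgb-in-range and blood-pressure exacerbation tests all use it. The type-I-controlled test of vitality is the baseline-adjusted ANCOVA. All of that stands, and it limits the point to efficiency. It does not remove the gain. Protocol 10.4.2.1 itself included baseline Hgb in the CMH test for the Hgb-increase responder endpoint, so adjusting a change-from-baseline responder test is not foreign to this trial.

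A reader might go further and infer that the responder analysis exists to interpret the principal secondary result, and that its different adjustment could make the two disagree needlessly. The documents do not support this. SAP Table 1 introduces the endpoint only as a further way to analyse SF-36 scores, and SAP 7.3.2.1 sends clinically meaningful effects to a separate reimbursement plan. The drop from 79% (step 1) to about 59% (step 2), both computed without baseline, comes from dichotomising. Disagreement would remain likely after the fix.

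**Conclusion.** The point holds as an optional efficiency improvement. At the plan's vitality inputs and an assumed correlation of 0.5, region-only CMH has about 58–59% power, and including baseline adds roughly 4 to 8 points: the lower part of that range with stratified CMH, the upper with a logistic model. The gain is about 3 to 5 points at 0.7 (one 3,000-trial logistic run rounds to 6; the formula gives 4.3) and 9 to 12 at 0.3. The result depends mainly on the correlation, which the documents do not give; it barely moves with the assumed placebo mean change.

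Two stronger readings should be avoided. The planned test is not biased and does not inflate type I error. Nor does the trial lose planned power: none is stated for this endpoint, it is nominal only, and the primary and principal secondary tests are untouched.

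**What to change.** In SAP 7.3.2.1, analyse the ≥ 6-point responder endpoint with a logistic model containing treatment, region and continuous baseline vitality. Report the covariate-standardised relative response rate with its 95% CI and one-sided p-value, so that the planned summary remains a relative response rate and not an odds ratio. Compute the log ratio and its standard error in each of the 200 imputed datasets and pool on the log scale by Rubin's rules.

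If CMH is preferred, add a baseline-vitality category to the region strata. Quartiles give 5 × 4 = 20 strata, and the SAP should say how the cut-points are set when baseline itself is imputed (SAP 10.6.3 creates rows for missing baseline scores).

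The cost is SAP wording, a delta-method or similar variance in each imputation, and a display slightly different from the SAP's other CMH responder tables. No new data are needed, and the raw percentages by arm stay in the table.
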